## 8.2 STATISTICAL ANALYSES

Analyses will be provided overall and by subgroup defined in section 5.3.

### Safety analyses

The safety analysis will be performed on the SAF population. AEs will be listed based on data recorded in the eCRF. A flag will be added to the AEs listing to identify patients who meet eligibility (inclusion/exclusion) criteria and with a radionuclide bone scintigraphy and/or SPECT performed with 99mTc-DPD/99mTc-PYP/99mTc-HMDP. No statistical test will be performed.

### Analysis of primary and secondary objectives

For each objective, a percentage/prevalence with its 95%CI will be assessed overall and in the sub-groups defined in section 5.3 if pertinent.

Endpoints	Population or Subgroup
Percentage of patients with cardiac fixation at the radionuclide bone scintigraphy and/or SPECT performed with 99m Tc-DPD or 99m Tc-PYP or 99m Tc-HMDP among patients with (left ventricular hypertrophy) LVH from an undiagnosed etiology	FAS1
Prevalence of Transthyretin amyloid (ATTR) or patients with suspicion of MGUS / AL amyloidosis	FAS1
Prevalence of hereditary (ATTRv) and wild-type (ATTRwt) ATTR amyloidosis in patients with positive scintigraphy	FAS2 & 3 (including 3.1 and 3.2)
Prevalence of TTR genetic mutation in patients with positive scintigraphy	FAS2 & 3 (including 3.1 and 3.2)
Prevalence of patients with familial history of known cardiomyopathy (CM), polyneuropathy (PN), sudden cardiac death (SCD) among their relatives (parents, siblings and 2 nd /3 rd grade family)	FAS1, 2 & 3 (including 3.1, 3.1(ATTRv), 3.1(ATTRwt) and 3.2)
Prevalence of patients with Senso-motor Polyneuropathy	FAS2 & 3 (including 3.1, 3.1(ATTRv), 3.1(ATTRwt) and 3.2)

PFIZER CONFIDENTIAL

Endpoints	Population or Subgroup
Prevalence of patients with CTS	FAS2 & 3 (including 3.1, 3.1(ATTRv), 3.1(ATTRwt) and 3.2)
Prevalence of patients with autonomic dysfunction	FAS2 & 3 (including 3.1, 3.1(ATTRv), 3.1(ATTRwt) and 3.2)
Prevalence of patients with cardiological manifestations	FAS2 & 3 (including 3.1, 3.1(ATTRv), 3.1(ATTRwt) and 3.2)
Prevalence of patients with laboratory signs	FAS2 & 3 (including 3.1, 3.1(ATTRv), 3.1(ATTRwt) and 3.2)
Description of the clinical and biochemical characteristics between patients with positive scintigraphy (cardiac fixation at the bone scintigraphy grade 1, 2 or 3) and/or SPECT (See section 0 § 3).	FAS2 & 3 (including 3.1, 3.1(ATTRv), 3.1(ATTRwt) and 3.2)
Discrepancy in the evaluation of the scintigraphy and/or SPECT images by different evaluators (See section 0 § 7)	FAS1

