### **Secondary objectives**

- To assess the prevalence of AL or ATTR amyloidosis in patients with cardiac fixation at the bone scintigraphy (visual grade 1 to 3) and/or SPECT;
- In patients diagnosed with ATTR Amyloidosis to assess the prevalence of hereditary (ATTRv) and wild-type (ATTRwt) ATTR amyloidosis;
- To describe TTR genetic mutations\*\* in patients with ATTRv amyloidosis;
- To assess the prevalence of patients with familial history of known cardiomyopathy (CM), polyneuropathy (PN), sudden cardiac death (SCD) among their relatives (ie, parents, siblings and 2nd /3rd degree family members).

[figure not shown]
- To assess the prevalence in patients with positive cardiac fixation at the bone scintigraphy and/or SPECT of patients with concomitant signs or symptoms of ATTR amyloidosis, ie,:
  - Sensori-motor Polyneuropathy (PN);
  - Carpal Tunnel syndrome (CTS);
  - Autonomic dysfunction;
  - Cardiological manifestations;
  - Laboratory signs;
  - Others.
- To compare the clinical and biochemical characteristics between patients with positive scintigraphy (cardiac fixation at the bone scintigraphy grade 1, 2 or 3) and/or SPECT.
- To assess the level of discrepancy in the evaluation of the scintigraphy and/or SPECT images by different evaluators

\* Bisphosphonate (99mTc-DPD/99mTc-PYP/99mTc-HMDP) Scintigraphy.

\*\* Variant and pathogenic mutation per sequencing the coding parts.

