## 2 INTRODUCTION

Note: in this document any text taken directly from the non-interventional (NI) study protocol is *italicised*.

*The main purpose of this study is to determine the prevalence of transthyretin amyloid cardiomyopathy (ATTR-CM) among patients admitted due to left ventricular hypertrophy (LVH) of unknown etiology when radionuclide bone scintigraphy or single photon emission computed tomography (SPECT) is used.*

[figure not shown]

Figure 1. Diagnostic algorithm for patients with suspected amyloid cardiomyopathy (Gillmore 2016).

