### 2. Secondary objectives

- *To assess the prevalence of Light Chain Amyloidosis (AL) or Transthyretin amyloid (ATTR) amyloidosis in patients with cardiac fixation at the bone scintigraphy (visual grade 1 to 3) and/or SPECT;*
- *To assess the prevalence of hereditary (ATTRv) and wild-type (ATTRwt) ATTR amyloidosis in patients diagnosed with ATTR amyloidosis;*
- *To describe TTR genetic mutations\*\* in patients with ATTRv amyloidosis;*
- *To assess the prevalence of patients with familial history of known cardiomyopathy (CM), polyneuropathy (PN), sudden cardiac death (SCD) among their relatives (ie, parents, siblings and 2nd/3rd degree grade family members);*
- *To assess the prevalence in patients with cardiac fixation at the bone scintigraphy or SPECT of concomitant signs or symptoms of ATTR amyloidosis, ie,:*
  - *Sensori-motor Polyneuropathy (PN);*
  - *Carpal Tunnel syndrome (CTS);*
  - *Autonomic dysfunction;*
  - *Cardiological manifestations;*
  - *Laboratory signs;*
- *To compare the clinical and biochemical characteristics between patients with positive scintigraphy (cardiac fixation at the bone scintigraphy grade 1, 2 or 3) and/or SPECT;*
- *To assess the level of discrepancy in the evaluation of the scintigraphy and/or SPECT images by different evaluators.*

\* *Bisphosphonate (99mTc-DPD/99mTc-PYP/99mTc-HMDP) Scintigraphy*

\*\* *Variant and pathogenic mutation by sequencing the coding parts*

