## 5 ANALYSIS SETS/POPULATIONS

### 5.1 FULL ANALYSIS SET

#### **Full Analysis Set 1 – Primary population**

Full Analysis Set 1 (FAS1) includes all patients who meet eligibility (inclusion/exclusion) criteria and with a radionuclide bone scintigraphy and/or SPECT performed with 99mTc-DPD/99mTc-PYP/99mTc-HMDP.

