#### **Full Analysis Set 2 – All FAS1 patients with positive scintigraphy (grade 1, 2 or 3)**

Full Analysis Set 2 (FAS2) is a subset of FAS1 patients with grading of cardiac retention equal to grade 1, grade 2 or grade 3.

Analysis of group 1 vs group 2&3 independently and grouped will be performed. Patients with grade 1 will be considered as “undetermined etiology”

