### 6.3 OTHER ENDPOINTS

#### Primary endpoint

Patients with cardiac fixation at the radionuclide bone scintigraphy and/or SPECT performed with 99mTc-DPD or 99mTc-PYP or 99mTc-HMDP will be defined as patients with a cardiac retention of grade 1, grade 2 or grade 3.

Patients without cardiac fixation at the radionuclide bone scintigraphy performed and/or SPECT with 99mTc-DPD or 99mTc-PYP or 99mTc-HMDP will be defined as patients with a cardiac retention of grade 0.

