#### Secondary endpoints

##### 1. Presence of Transthyretin amyloid (ATTR) or patients with suspicion of MGUS / Light Chain Amyloidosis (AL)

- Patients with grade 2 or 3 at scintigraphy will be considered “Cardiac amyloidosis patients”
  - Patients with grade 2 or 3 at scintigraphy without monoclonal protein abnormalities will be considered patients with **ATTR amyloidosis**
  - Patients with grade 2 or 3 at scintigraphy with monoclonal protein abnormalities will be considered of the population of **patients with suspicion of MGUS or AL amyloidosis**
- Patients with grade 1 at scintigraphy will be considered as “**undetermined**”

Monoclonal protein abnormalities are defined as patients with positive IFE (Immunofixation electrophoresis) (serum and urine) or with abnormal FLC (free light chain) ratio:

	eGFR			
	>60	45-<60	30-<45	<30
Abnormal FLC ratio	≥1.65	≥1.92	≥2.06	≥2.17
Normal FLC ratio	<1.65	<1.92	<2.06	<2.17

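### The first secondary objective asks for AL/ATTR prevalence among patients with cardiac fixation, but the SAP plans that estimate only in FAS1

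*SAP*

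**What the plan says.** Protocol section 8 words the objective as "To assess the prevalence of AL or ATTR amyloidosis in patients with cardiac fixation at the bone scintigraphy (visual grade 1 to 3) and/or SPECT". The protocol's title-page table and abstract set the same denominator, and so does SAP 2.2, which asks for the prevalence "in patients with cardiac fixation at the bone scintigraphy (visual grade 1 to 3) and/or SPECT".

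The endpoint table in SAP 8.2 carries this as "Prevalence of Transthyretin amyloid (ATTR) or patients with suspicion of MGUS / AL amyloidosis", and its population column reads FAS1. SAP 5.1 says that FAS1 "includes all patients who meet eligibility (inclusion/exclusion) criteria and with a radionuclide bone scintigraphy and/or SPECT performed". FAS2 "is a subset of FAS1 patients with grading of cardiac retention equal to grade 1, grade 2 or grade 3", and the primary endpoint in SAP 6.3 uses the same grades: patients with cardiac fixation "will be defined as patients with a cardiac retention of grade 1, grade 2 or grade 3".

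For the numerator, SAP 6.3 reads "Patients with grade 2 or 3 at scintigraphy without monoclonal protein abnormalities will be considered patients with" ATTR amyloidosis. Grade 2 or 3 with a monoclonal abnormality becomes suspected MGUS or AL, and grade 1 is undetermined.

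SAP section 2 gives the main purpose as "to determine the prevalence of transthyretin amyloid cardiomyopathy (ATTR-CM) among patients admitted due to left ventricular hypertrophy (LVH) of unknown etiology".

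**The concern.** The objective and the planned analysis have different denominators. One asks what a positive scan turns out to be; the other asks how common ATTR is among all scanned patients with unexplained LVH. If the table is programmed as it stands, the report will put a percentage with a confidence interval against the first secondary objective that does not estimate what the objective describes. A reader who takes it at face value would greatly understate the share of positive scans that are ATTR.

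The next rows of the same table (hereditary and wild-type ATTR, mutations, signs and symptoms) are assigned to FAS2 and FAS3, and family history to FAS1, 2 and 3. The authors therefore listed several sets elsewhere, but not in this row.

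**Working it through.** **1. Is the estimate planned elsewhere?** SAP 8.2 promises each objective a percentage with a 95% CI, overall and in the section 5.3 subgroups. Those subgroups are only ATTRv and ATTRwt, so they add no FAS2 estimate. Item 3 of *Other analyses* describes CRF variables by red-flag count, grade and genotype. It does not give the ATTR or suspected-AL share of FAS2. The FAS 2&3 table shell in SAP section 9 shows column counts for FAS 3.1, FAS 3.2 and the FAS2 total, so the ratio could be formed by hand, but no CI is planned.

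**2. The plan's own precision figures.** Protocol 9.5 assumes 10% ATTR-CM, N = 1500, and a sign frequency of 30% among the resulting 0.10 × 1500 = 150 patients. The half-width is 1.96 × √(p(1−p)/n):
- p = 0.10, n = 1500: 1.52 points (stated ±1.5%).
- p = 0.30, n = 150: 7.33 points (stated ±7.3%).

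Both reproduce. The denominator finding does not depend on them, but they fix the premise used below.

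**3. The FAS1 row.** SAP 8.1 specifies the Wilson interval: [p + z²/2n ± z√(p(1−p)/n + z²/4n²)] / (1 + z²/n). With 150/1500, the centre is (0.1000 + 0.00128)/1.00256 = 0.1010 and the half-width is 0.0152. The result is 10.0% (8.6 to 11.6), whatever share of patients shows fixation.

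**4. The figure the objective asks for.** ATTR requires grade 2 or 3, so every ATTR patient lies in FAS2, and the FAS2 percentage equals the FAS1 percentage divided by the share with fixation. The documents do not give that share. If ATTR-CM is 10%, it cannot be below 10%. The values below, 12% to 25%, are assumptions for illustration.

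| Assumed share with fixation | N = 1500: ATTR / FAS2 | FAS2 figure (Wilson 95% CI) | Ratio to FAS1 figure |
|---|---|---|---|
| 12% | 150/180 | 83.3% (77.2 to 88.1) | 8.3 |
| 15% | 150/225 | 66.7% (60.3 to 72.5) | 6.7 |
| 20% | 150/300 | 50.0% (44.4 to 55.6) | 5.0 |
| 25% | 150/375 | 40.0% (35.2 to 45.0) | 4.0 |

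The abstract's milestone table also allows data collection to end at 1000 screened patients. With 100 ATTR patients in 1000, FAS1 gives 10.0% (8.3 to 12.0), and FAS2 runs from 83.3% (75.7 to 88.9) at a 12% share to 40.0% (34.1 to 46.2) at 25%.

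**5. Counting rules the row leaves open.**
- *Grade 0.* SAP 6.3 classifies only grades 1 to 3 for this endpoint, and SAP 8.1 bases percentages on filled data. The natural reading is that grade 0 counts as neither ATTR nor AL. If a programmer left it blank, those patients would drop out of the denominator and the row labelled FAS1 would return the FAS2 figure.
- *Untested grade 2-3.* Protocol 9.2.4 collects monoclonal results only if the tests were done, and SAP section 7 imputes nothing. The SAP does not say whether an untested patient counts as ATTR, is left out, or is shown separately. This affects both denominators.
- *SPECT-only positives.* The objective includes fixation on SPECT. FAS2 is defined by grade, whereas protocol 9.3 lists the SPECT result as a variable separate from the grade.
- *AL.* The objective names AL; the endpoint estimates suspected MGUS or AL, and SAP 5.1 allows that FAS 3.2 may include ATTR. AL prevalence as such is not estimated in either set.

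**The case against.** The best defence is that FAS1 is a sensible population for this row. The main purpose, in protocol section 7 and SAP section 2, is ATTR-CM prevalence among patients with unexplained LVH, and protocol 9.5 sizes the study on that quantity. This stands: FAS1 should stay, and a reader who infers that the FAS1 analysis is itself wrong goes further than the documents allow.

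A reader might also infer that FAS1 is distorted because monoclonal results are not collected for scan-negative patients. That does not follow. Under SAP 6.3 both ATTR and suspected MGUS/AL require grade 2 or 3, so a grade 0 patient cannot enter either numerator whatever the monoclonal status. Missing tests matter in grade 2-3 patients, and equally in both sets.

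It is also fair to say that the missing percentage can largely be recovered from counts in the planned tables, that the full table list is a separate document not available here, and that SAP 4.1 and 4.2 describe a mainly descriptive study with exploratory tests. These points limit the harm. They do not supply a pre-specified estimate with an interval for a written objective, and the visible SAP text assigns FAS1 only.

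**Conclusion.** The concern holds as an omission: the SAP does not plan the estimate that the first secondary objective names. It does plan a different and useful one. The primary endpoint is unaffected, and the correction is worth making because the objective otherwise has no matching result.

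The gap between the two figures is large, but the documents do not support a single multiple. It is the reciprocal of the share with fixation, which they do not state. At 10% ATTR-CM and an assumed share of 12% to 25%, 10.0% in FAS1 corresponds to between 83.3% and 40.0% in FAS2, a factor of 8.3 down to 4. These figures also assume that every grade 2-3 patient can be classified from monoclonal tests. The intervals of the two estimates describe different quantities, so the wider FAS2 interval does not measure harm.

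**What to change.** In the SAP 8.2 endpoint table:

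1. Assign this objective to FAS2, and state that FAS2 means all patients with cardiac fixation, including any positive on SPECT only.
2. Keep FAS1 as a separate row labelled *ATTR-CM prevalence in unexplained LVH (main purpose)*.
3. Give a Wilson 95% CI for each row.

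In SAP 6.3, add these counting rules:

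- Grade 0 counts as non-ATTR and non-AL in the FAS1 row.
- Grade 2-3 patients without monoclonal testing are reported as a separate *untyped* category, not as ATTR.
- The second category is labelled *suspected MGUS/AL* and is not presented as AL prevalence.

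The cost is one changed table cell, one extra output and a few sentences; no new data are needed. The FAS2 figure will have a wider interval: under the assumptions above with N = 1500, a half-width of about 5 to 6 points, against 1.5 for FAS1.

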## **Other analyses**

### **1. Patient characteristics**

A full description of patient characteristics will be provided in the FAS1.

### **2. Analysis of redflags**

The prevalence of each redflag will be assessed in the FAS 1, 2 & 3 population.

PFIZER CONFIDENTIAL

### 3. Description of variables of interest

Variables of interest are all variables collected in the CRF (including Kappa, Lambda, IgG, IgA and IgM rates from monoclonal protein studies).

- Variables of interest will be described in the FAS2 & 3 population in patients with 1, 2 or 3 redflags.
- Variables of interest will be described in the FAS1 population in patients with grade 0/1/2/3.
- Variables of interest will be described in the FAS2 & 3 population in patients with ATTRv and ATTRwt.

### 4. Comparison between patients with final diagnosis of ATTR-CM and screened patients

Patients with a final diagnosis of ATTR-CM will be compared with the other “negative” screened patients in order to highlight possible diagnostic TTR-Amyolosis red flags

### 5. Factors associated to positive scintigraphy

Factors associated to positive scintigraphy will be identified in the FAS1 by univariate and multivariate logistic regression. This analysis will be performed in the FAS1 population and will include all variables collected in the CRF for both positive and negative scintigraphy. Clinical laboratories will be excluded from this analysis as only available for positive scintigraphy.

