## 9.3. Variables

Variable	Data source(s)
Patient informed consent date	PATIENT INCLUSION
Patient visit date	PATIENT INCLUSION
Age ≥50 years	PATIENT INCLUSION
LVH Echo demonstrated end-diastolic LV MWT ≥15mm	PATIENT INCLUSION
Maximal end diastolic wall thickness	PATIENT INCLUSION
Sarcomeric HCM (Genetic testing)	PATIENT INCLUSION
Plasma cell dyscrasia	PATIENT INCLUSION
Fabry disease	PATIENT INCLUSION
AL, AA or any other amyloidosis	PATIENT INCLUSION
Severe aortic stenosis (defined as) Maximal aortic velocity >4 m/s or Mean gradient >40 mmHg	PATIENT INCLUSION
Birth date (mm-yyyy)	PATIENT INFORMATION
Gender	PATIENT INFORMATION
Weight	PATIENT INFORMATION
Height	PATIENT INFORMATION
Ethnic Origin	PATIENT INFORMATION
Date	CLINICAL EVALUATION
Diastolic blood pressure	CLINICAL EVALUATION
Systolic blood pressure	CLINICAL EVALUATION
Diagnosed hypertension	CLINICAL EVALUATION
Antihypertensive medication	CLINICAL EVALUATION
Coronary artery disease	CLINICAL EVALUATION
Renal insufficiency	CLINICAL EVALUATION
Diabetes Mellitus	CLINICAL EVALUATION
Lumbar spinal stenosis 1	CLINICAL EVALUATION
CTS – surgery history 2	CLINICAL EVALUATION
New York heart Association (NYHA) class	CLINICAL EVALUATION
Atrial Fibrillation (AF)	CLINICAL EVALUATION

Variable	Data source(s)
Pacemaker	CLINICAL EVALUATION
AICD (Automatic Implantable Cardiac Defibrillator)	CLINICAL EVALUATION
LGE (Late Gadolinium Enhancement)	CLINICAL EVALUATION
Heart rate	CLINICAL EVALUATION
Sinus rhythm	CLINICAL EVALUATION
PR Interval	CLINICAL EVALUATION
QRS interval	CLINICAL EVALUATION
Sokolow index	CLINICAL EVALUATION
Pseudo-MI pattern	CLINICAL EVALUATION
Poor precordial R wave progression	CLINICAL EVALUATION
LBBB RBBB Paced Intraventricular conduct delay	CLINICAL EVALUATION
Left Ventricular Ejection Fraction (LVEF)	CLINICAL EVALUATION
Left Ventricular Obstruction Tract (LVOT)	CLINICAL EVALUATION
Longitudinal strain done?	CLINICAL EVALUATION
LV end-diastolic diameter	CLINICAL EVALUATION
MWT	CLINICAL EVALUATION
MWT at septum	CLINICAL EVALUATION
MWT posterior wall	CLINICAL EVALUATION
Hypertrophic pattern Apical, Concentric, Asymmetric, Mix	CLINICAL EVALUATION
LV mass index	CLINICAL EVALUATION

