#### 9.5. Study Size

Considering a prevalence of ATTR-CM around 10%, the screening of N =1500 patients will provide a precision of  $\pm 1.5\%$  in the estimation of this prevalence with a 95% two-sided confidence interval (first objective). In addition, considering such a prevalence, the precision of the estimation of the different symptoms or additional signs within the population of ATTR-CM (other objectives) will be estimated with a precision of  $\pm 7.3\%$  for any sign/symptom with a frequency of 30% or lower.

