### 6. Factors associated to grade 2-3 scintigraphy and ATTR-CM

Factors associated to grade 2 or 3 will be identified in the FAS1 by univariate and multivariate logistic regression (compared with negative patients). This analysis will be performed in the FAS1 population and will include all variables collected in the CRF for both positive and negative scintigraphy. Clinical laboratories will be excluded from this analysis as only available for positive scintigraphy. The same analysis will be repeated to identify factors associated to ATTR-CM (FAS 2 & 3).

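### Paced and non-paced ECGs are pooled, so unequal pacing could appear as an ECG difference in the by-grade tables and univariate odds ratios

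*SAP*

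**What the plan says.** Protocol 9.3 (Variables) collects PR interval, QRS interval, Sokolow index, pseudo-infarction pattern and R-wave progression under clinical evaluation. Pacemaker and AICD are separate items, and pacing on the ECG is recorded in the row "LBBB RBBB Paced Intraventricular conduct delay".

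Three analyses in SAP 8.2 (Other analyses) use these data:

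- Item 3: "Variables of interest will be described in the FAS1 population in patients with grade 0/1/2/3", where the variables of interest are everything in the CRF.
- Item 5: the model for a positive scan "will include all variables collected in the CRF for both positive and negative scintigraphy".
- Item 6: the model for grade 2–3, repeated for ATTR-CM, has the same scope.

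The only exclusion in items 5 and 6 concerns laboratory data: "Clinical laboratories will be excluded from this analysis as only available for positive scintigraphy".

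SAP 8.1 fits one logistic model per factor, carries factors significant at 10% into a multivariate model, removes them backwards at 5%, and tests interactions. Univariate and multivariate odds ratios are both reported, in separate columns of table shell 15.2.2.

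**The concern.** In a ventricularly paced ECG, QRS width, voltage and R-wave progression describe the device, not the diseased myocardium. If scan-positive patients are paced more often, each of these variables carries the pacing difference into its grade table and its one-factor odds ratio.

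The documents make such an imbalance plausible. Protocol section 7 describes conduction disorders as part of ATTR amyloidosis, and SAP 6.3 item 7 counts Pacemaker and Paced among the cardiological manifestations. They give no pacing frequency by scan result.

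The affected output is meant to be used. Protocol 9.7 and SAP 8.2 item 4 aim to find diagnostic red flags, and Protocol section 7 treats low voltage, the pseudo-infarction pattern and voltage relative to wall thickness as diagnostic information. A red flag produced by pacing would not help a clinician reading an intrinsic ECG, and pacing could equally hide a real voltage difference.

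**Working it through.** **The plan's own figures.** Protocol 9.5 says that "the screening of N =1500 patients will provide a precision of" ±1.5% at 10% prevalence, and ±7.3% "for any sign/symptom with a frequency of 30% or lower". Both reproduce with the half-width 1.96 × √(p(1 − p)/n):

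- p = 0.10, n = 1500: 1.52%.
- p = 0.30, n = 150: 7.33%.

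These figures do not concern pacing, but they set the group sizes. Taking 10% as the share of positive scans gives 150 vs 1350 at N = 1500. The milestones in the protocol abstract allow data collection to end at 1000 screened, which gives 100 vs 900.

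**Assumptions not in the documents.** Intrinsic QRS mean 105 ms, paced mean 160 ms, SD 20 ms in both; 5% of scan-negative patients paced; 5%, 10%, 15% or 20% of scan-positive patients paced; no true link between intrinsic QRS and scan result.

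**Mean difference from pacing alone.** (share paced in positives − share paced in negatives) × (160 − 105):

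- 10% vs 5%: 0.05 × 55 = 2.75 ms.
- 15% vs 5%: 0.10 × 55 = 5.5 ms.
- 20% vs 5%: 0.15 × 55 = 8.25 ms.

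**Simulation.** Each run used 600 data sets and logistic regression of scan status on QRS. The last column applies the SAP's rule (10% screen, then 5% backward) with QRS and 'Paced' as the two candidates. Ranges span separate runs.

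| Paced, positive vs negative | Univariate p < 0.10, 100 vs 900 | Univariate p < 0.10, 150 vs 1350 | Univariate OR per 10 ms, 150 vs 1350 | QRS in final model, 150 vs 1350 |
|---|---|---|---|---|
| 5% vs 5% | 11% | 10% | 1.00 | 4.8% |
| 10% vs 5% | 29–32% | 39–40% | 1.05 | 8.5% |
| 15% vs 5% | 65–68% | 77–84% | 1.09 | 4.7% |
| 20% vs 5% | 90–92% | 97% | 1.14 | 3.5% |

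**After a correction.** With paced ECGs removed, the 10% screen is passed in 9–14% of runs at 100 vs 900, and p < 0.05 occurs in 4.2–5.8% at 150 vs 1350. With 'Paced' as a covariate, QRS has p < 0.05 in 4.2–6.0% of runs at 150 vs 1350, with an odds ratio of 0.997–1.002 per 10 ms. Either route restores roughly nominal behaviour.

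**The case against.** The strongest reply is that the multivariate model already handles this. Pacemaker, AICD and 'Paced' are CRF variables, so they compete in the same models. The last column of the table bears this out: retention of QRS is close to 5% except at 10% vs 5% paced, where it is 8.5%. A reader might infer that the plan's final models will present pacing as a QRS marker; the documents and the calculation do not support that. What remains is that the protection is not prespecified. 'Paced' must survive selection, and the two-candidate simulation does not test whether correlated factors such as sinus rhythm or bundle branch block could displace it.

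Four further points stand as limits:

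- The imbalance is assumed. With equal pacing there is no artefact.
- The CRF (Appendix 3) is a stand-alone document not available here. If it leaves these fields blank on paced ECGs, SAP section 7 does not impute them and they already drop out of their univariate models.
- SAP 4.2 declares all tests exploratory.
- Unadjusted tables carry every confounder by design, and the same tables will show paced status by grade.

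The last point softens the problem without removing it: a reader can see unequal pacing but cannot recover the intrinsic-ECG comparison from pooled summaries.

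It is also fair that pacing may be a consequence of the disease, so restricting to non-paced ECGs selects on that consequence. This is why pacing should stay as a factor in all patients. Finally, the 'Paced' item as listed does not name the paced chamber, so a filter may drop some ECGs whose QRS is intrinsic.

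**Conclusion.** The point holds for the descriptive and univariate output. SAP 8.2 items 3, 5 and 6 pool paced and non-paced ECGs, and a moderate pacing imbalance would be enough to make QRS pass the univariate screen far more often than the nominal 10%: about 30%, 68% and 90% of runs at 100 vs 900 in the three unequal scenarios. These figures rest entirely on the assumed QRS values and pacing shares.

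For the final multivariate model the effect is small, with QRS retained in about 4–9% of runs against 5% nominal.

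Only QRS is quantified here. The same reasoning applies to PR, Sokolow index, pseudo-infarction pattern and R-wave progression, but the documents do not settle the direction for voltage. A reader might also infer that the primary result is at risk. It is not: the prevalence of cardiac fixation uses no ECG variable. The change is worth making because the affected tables are meant to suggest red flags and the item needed is already collected.

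**What to change.** Add to SAP 8.2 items 3, 5 and 6:

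1. Report the number and percentage with 'Paced' ticked, by grade.
2. Describe QRS, PR, Sokolow index, pseudo-infarction pattern and R-wave progression, and fit their univariate models, only in ECGs not ticked 'Paced'.
3. Keep Pacemaker and Paced as factors in their own right in all patients.
4. Force 'Paced' into any multivariate model that contains one of these ECG variables, or show a model restricted to non-paced ECGs as a sensitivity analysis.

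State also whether the CRF accepts these measurements on paced ECGs.

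The cost is SAP wording and a filter on an existing item; no new data are needed. The ECG rows lose patients: at 100 vs 900 with 15% vs 5% paced, 0.15 × 100 = 15 positives and 0.05 × 900 = 45 negatives leave, so 85 and 855 remain. Results from the restricted analyses then apply to non-paced patients only, and the report should say so.
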